12.3. Protocol Deviations/Violations

If the Investigator desires to modify the procedures and/or design of the study, he or she must contact and obtain the consent and approval of Ocuphire and the IRB, regarding the proposed changes, prior to their implementation. Changes implemented after obtaining this approval will be considered Protocol Deviations. Changes implemented without prior approval will be considered Protocol Violations.

12.4. Informed consent requirements

Written informed consent will be obtained from each subject. A copy of the signed and dated consent document will be given to each subject. The original signed and dated informed consent document must be maintained in the study files at the Investigator's site.

The investigator is responsible for ensuring that no subject is subject to any study-related examination or activity before that subject has given informed consent. The subject must give written consent after the receipt of detailed information. The verbal explanation will cover all the elements specified in the written information provided for the subject.

It should be emphasized that the subject is at liberty to withdraw consent to participate at any time, without penalty or loss of benefits to which the subject is otherwise entitled. Subjects who refuse to give, or withdraw, written informed consent may not be included or continued in this study, but this will not impact on their subsequent care.

The investigator will inform the subject of the aims, methods, anticipated benefits and potential hazards of the study, including any discomfort it may entail. The subject must be given every opportunity to clarify any points he/she does not understand and if necessary, ask for more information. At the end of the interview, the subject may be given time to reflect if this is required, or if the subject requests more time. Subjects and/or legal guardian will be required to sign and date the informed consent form.

A copy of the signed and dated consent document will be given to each subject. The original signed and dated informed consent document must be maintained in the study files at the Investigator's site. Signed informed consent must be obtained prior to the conductance of any study procedures.

13. DATA HANDLING AND RECORD KEEPING

All procedures for the handling and analysis of data will be conducted using good computing practices meeting ICH and U.S. Food and Drug Administration (FDA) guidelines for the handling and analysis of data for clinical trials.

13.1. Data Entry

All study data will be entered into a paper CRF. CRFs are considered to be the source documents for this study. Data will be entered from the CRF into the study database.

13.2. Data quality control and reporting

After data have been entered into the study database, a system of computerized data validation checks will be implemented and applied to the database. Query reports pertaining to data omissions and discrepancies will be forwarded to the Clinical Investigator and Ocuphire for resolution. The study database will be updated in accordance with the resolved query reports. All changes to the study database will be documented.

13.3. Archiving of data

Archived versions of the database will be saved by Ocuphire consistent with ICH Good Clinical Practices Guidelines, complying with whichever of the requirements is longer. Ocuphire will notify the investigator when documents should be returned.

13.4. Records retention

The Investigator's site and clinical laboratory will retain all records related to the study in compliance with ICH Good Clinical Practices Guidelines.

13.5. Amendments to the protocol

Modifications of the signed protocol are only possible by approved protocol amendments and with the agreement of all responsible persons. The procedure for approval of a protocol amendment is identical to that for approval of the protocol. The IRB must be informed of all protocol amendments and should be asked for its opinion as to whether a full re-evaluation of the ethical aspects of the study is necessary by the committee. This should be fully documented.

The investigator must not implement any deviation from or change to the protocol, without discussion with, and agreement by Ocuphire and prior review and documented approval/favorable opinion of the amendment from the relevant ethics committee, except where it is necessary to eliminate an immediate hazard to study subjects, or where the change(s) involves only logistical or administrative aspects of the study [e.g., change in monitor(s), change of telephone number(s)].

Protocol amendments will be submitted to the appropriate authority(ies) as required by the applicable regulatory requirement(s).

## 2. LIST OF ABBREVIATIONS AND DEFINITION OF TERMS

Only abbreviations and terms relevant to the SAP are repeated herein. The reader is referred to the protocol for the complete and comprehensive list of abbreviations and definitions of terms for the study.

Abbreviation/Term	Definition
ADaM	Analysis Data Model
AE	Adverse Event
AM	Ante Meridian – in the morning
ANCOVA	Analysis of Covariance
AR	All Randomized
ATC	Anatomical Therapeutic Chemical
BCDVA	Best Corrected Distance Visual Acuity
BP	Blood Pressure
CCLRU	Cornea and Contact Lens Research Unit
CDISC	Clinical Data Interchange Standards Consortium
CI	Confidence Interval
CRF	Case Report Form
CSR	Clinical Study Report
DCNVA	Distance Corrected Near Visual Acuity
DD	Drug Dictionary
ETDRS	Early Treatment Diabetic Retinopathy Study
FAS	Full Analysis Set
FDA	Food and Drug Administration
HR	Heart Rate
ICH	International Council for Harmonisation
IOP	Intraocular Pressure
IRB	Institutional Review Board
ITT	Intent-To-Treat
LSM	Least Squares Mean
LOCF	Last Observation Carried Forward
logMAR	logarithm of the Minimum Angle of Resolution
m	meter
MAR	Missing at Random
MCMC	Markov Chain Monte Carlo

Abbreviation/Term	Definition
mmHg	millimeters of mercury
MedDRA	Medical Dictionary for Regulatory Activities
Nyxol	Phentolamine Mesylate Ophthalmic Solution 1 % (Nyxol®)
OAG	Open Angle Glaucoma
OD	Right eye
OHT	Ocular Hypertension
OR	Odds Ratio
OS	Left eye
OU	Both eyes
PM	Post Meridian
PP	Per Protocol
PT	Preferred Term
QD	Once daily
SAE	Serious Adverse Event
SAP	Statistical Analysis Plan
SDTM	Study Data Tabulation Model
SE	Standard Error
SOC	System Organ Class
SOP	Standard Operating Procedure
SP	Safety Population
TEAE	Treatment Emergent Adverse Event
TFL	Tables, Figures, and Listings
US	United States
VA	Visual Acuity
WHO	World Health Organization

### **3. INTRODUCTION**

#### **3.1. Preface**

This document presents a statistical analysis plan (SAP) for Ocuphire Pharma, Inc. Protocol OPI-NYXG-201 (ORION-1) (*Randomized, Placebo-Controlled, Double-Masked Study of the Safety and Efficacy of Phentolamine Mesylate Ophthalmic Solution in Subjects with Open Angle Glaucoma or Ocular Hypertension*).

Reference materials for this statistical plan include the protocol OPI-NYXG-201 Amendment 1 (08APR2019) and Case Report Forms (Final Version 24APR2019).

The SAP described hereafter is an *a priori* plan. The SAP will be finalized and approved prior to unmasking of any study data.

For the reasons stated here the conduct of the study in the field is considered to be independent of any study outcome that might materialize upon enactment of the currently proposed statistical plan.

#### **3.2. Purpose of Analyses**

The purposes of the planned analyses described in this SAP are to evaluate the efficacy to lower intraocular pressure (IOP), to improve visual performance, and to evaluate the ocular and systemic safety of Nyxol Eye Drops - 1% Phentolamine Mesylate ophthalmic solution (Nyxol) compared to its vehicle, in Open Angle Glaucoma (OAG) and Ocular Hypertension (OHT). Results from the analyses completed will be included in the final clinical study report for OPI-NYXG-201, and may also be utilized for regulatory submissions, manuscripts, or other clinical development activities.

Post-hoc exploratory analyses not identified in this SAP may be performed to further examine the study data. These analyses will be clearly identified, where appropriate, in the final clinical study report. Additional analyses not prospectively identified in this SAP may also be completed for publications, or regulatory or funding inquiries. These analyses, if performed, may not be reported in the clinical study report, but will be fully documented in the document containing the additional analyses.

#### **3.3. Summary of Statistical Analysis Changes to the Protocol**

The analyses described in this analysis plan are consistent with the analyses described in the study protocol.

## **4. STUDY OBJECTIVES AND ENDPOINTS**

Study objectives and endpoints defined in the protocol include safety and efficacy endpoints. Objectives and pre-specified endpoints are as follows:

### **4.1. Study Objectives**

The objectives of this study are as follows:

- To evaluate the efficacy of Nyxol to lower IOP in OAG and OHT.
- To evaluate the ocular and systemic safety of Nyxol compared to its vehicle.
- To evaluate additional efficacy of Nyxol to improve visual performance.

### **4.2. Study Endpoints**

#### **4.2.1. Primary Endpoints**

The primary efficacy endpoint from the protocol is the change from Baseline to Day 15 in mean diurnal IOP in the study eye. Mean diurnal IOP is the mean of the IOP measurements at all three timepoints (8AM, 10AM, 4PM).

The primary safety measures are:

- Objective biomicroscopic and ophthalmoscopic examination
- Subjective ocular tolerability
- Adverse events (AEs)

#### **4.2.2. Secondary Endpoints**

Secondary endpoints for efficacy and safety assessments include the following:

Efficacy:

Secondary efficacy endpoints will be analyzed by study eye, fellow eye and all eyes (the pooled data from the study eye and fellow eye) unless otherwise indicated, and will include:

- Change from Baseline to Day 15 in mean diurnal IOP in the fellow eye and all eyes.
- Change from Baseline to Day 8 in mean diurnal IOP.
- Mean IOP at each post-treatment timepoint (8AM, 10AM and 4PM; on Day 8 and Day 15).
- Change and percent change from Baseline to Day 8 and Day 15 in IOP at each timepoint (8AM, 10AM, 4PM), and Day 16 at 8AM.

- Percentage of subjects achieving reductions from Baseline to Day 8 and Day 15 in IOP at 8AM of greater than or equal to 10%, 15%, 20%, 25% and 30%.
- Percentage of subjects achieving Day 8, Day 15 and Day 16 IOP levels at 8AM of less than or equal to 16mmHg, 18mmHg, 20mmHg and 22mmHg.
- Change and percent change from Baseline Day 8, Day 15, and Day 16 in IOP at 8AM.
- Change and percent change to Days 8, 15, and 16 in pupil diameter at 8AM.
- Percentage of subjects achieving reductions from Baseline to Day 8, Day 15 and Day 16 in pupil diameter at 8AM, of greater than or equal to 10%, 15%, 20%, 25%, and 30%.
- Change from Baseline to Day 8, Day 15, and Day 16 in best corrected distance visual acuity (BCDVA) (Early Treatment Diabetic Retinopathy Study [ETDRS] high contrast) (photopic and mesopic) at 8AM.
- Change from Baseline to Day 8, Day 15, and Day 16 in distance corrected near visual acuity (DCNVA) (ETDRS high contrast) (photopic and mesopic) at 8AM.
- Percentage of subjects achieving improvements from Baseline to Day 8, Day 15, and Day 16 in BCDVA and DCNVA (photopic and mesopic) of greater than or equal to 1 line, 2 lines and 3 lines. For BCDVA, only the number of letters read is collected; this will be converted to lines as follows: 1 line = 3-7 letters read; 2 lines = 8-12 letters read; 3 lines = 13-17 letters read, etc. For DCNVA, only the logMAR value is collected; this will be converted to lines as follows: 1 line = 1.3 logMAR; 2 lines = 1.2 logMAR; 3 lines = 1.1 logMAR, etc. to 14 lines = 0.0 logMAR, 15 lines = -0.1 logMAR, 16 lines = -0.2 logMAR, and 17 lines = -0.3 logMAR.

All secondary endpoints related to IOP will be analyzed additionally in those subpopulations with Baseline IOP of  $<25\text{mmHg}$  and  $\geq 25\text{mmHg}$ . Subjects will be categorized as " $<25\text{mmHg}$ " if their study eye Baseline IOP readings at all time points (8AM, 10AM, and 4PM) are  $<25\text{mmHg}$ .

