9. STATISTICS

9.1. *Sample Size*

A sample size of 36 total completed subjects is needed for the study. Thirty-six completed subjects, who were originally randomized in a 1:1 ratio to the Nyxol 1% and the placebo groups, [REDACTED]

[REDACTED] Additionally, it is assumed that there will be approximately 10% drop-out between Baseline/Day 1 and Day 15. To account for this drop-out, a total of 40 subjects will be randomized into the study.

9.2. *Analysis Populations*

Full Analysis Set (FAS): The FAS will include all randomized subjects who have received at least 11 doses of study medication without missing 2 consecutive doses and have both a Baseline and a Day 15 IOP measurement. This population is also known as the Per Protocol (PP) population. The FAS will be used to analyze efficacy endpoints.

All Randomized Population (AR): The AR population will include all randomized subjects. This population is also known as the intent-to-treat (ITT) population. The AR population will be used in confirmatory efficacy analyses.

Safety Population (SP): The SP will include all randomized subjects who have received at least one dose of study medication. The SP will be used to summarize safety variables.

9.3. *Statistical Methods*

9.3.1. **General Considerations**

All continuous variables will be summarized by treatment and timepoint (as applicable) using descriptive statistics (n, mean, median, standard deviation, minimum, and maximum). All categorical variables will be summarized by treatment and timepoint (as applicable) using frequency counts and percentages.

All study data will be listed by treatment, subject and timepoint (as applicable).

All statistical tests will be performed using a significance level of 5% (two-tailed). Given the large number of secondary efficacy endpoints, the p-values for those analyses will be considered descriptive.

9.3.2. **Demographic and Baseline Characteristics**

Demographic and Baseline characteristics such as age, race, gender, and history of ocular surgery and procedures, will be summarized by treatment group using the FAS and the AR population. These data will also be provided in by-subject listings.

9.3.3. **Subject Disposition**

Subject disposition, including randomization, and completion and withdrawal from the study will be summarized using the AR population. These data will also be provided in by-subject listings.

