## 6. SAMPLE SIZE

A sample size of 36 total completed subjects is needed for the study. Thirty-six completed subjects, who were originally randomized in a 1:1 ratio to the Nyxol 1% and the placebo groups,

additionally, it is assumed that there will be approximately 10% drop-out between Baseline/Day 1 and Day 15. To account for this drop-out, a total of 40 subjects will be randomized into the study.

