Secondary efficacy endpoints (for the study eye unless otherwise noted) are indicated in [Section 4.2.2](#). Secondary efficacy endpoints will be analyzed by study eye, fellow eye and all eyes (unless otherwise indicated). "All eyes" refers to the pooled data from the study eye and fellow eye, so there will be 2 results per subject for any summary of all eyes if the endpoint was assessed for both the study eye and fellow eye. Secondary efficacy assessments not related to IOP will be analyzed only at 8AM. Binocular near and distance VA assessments will not be analyzed. All secondary efficacy assessment data, regardless of whether they are included in the analysis, will be presented in by-subject listings.

For each of the continuous secondary efficacy endpoints, the same ANCOVA for the primary efficacy endpoint will be used, with the respective Baseline included as the covariate. Each ANCOVA will be performed using the FAS with subjects included in their randomized treatment group regardless of the treatment they actually received. The output from each ANCOVA will include the LSM and SE for both treatment groups, along with the placebo-corrected LSM (Nyxol – placebo), its 95% CI and associated p-value.

For each of the secondary efficacy endpoints related to percentage of subjects (or percentage of eyes) meeting certain criteria, the analysis will be performed for the FAS using a logistic regression with treatment and Baseline included as independent factors. For each analysis, the percentage of subjects (or eyes) in each treatment group meeting the criteria, the odds ratio (OR) with 95% CI and p-value will be provided.

For the analysis of the secondary efficacy endpoints, only observed case data will be used.

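### The SAP rounds BCDVA letters to the nearest line before counting line gains, so gains under 5 letters can count and the starting score decides which do

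*SAP*

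**What the plan says.** SAP 4.2.2 lists, as a secondary efficacy endpoint, the percentage of subjects improving from Baseline by at least 1, 2 and 3 lines in BCDVA and DCNVA on Days 8, 15 and 16. It then adds a conversion rule: "For BCDVA, only the number of letters read is collected; this will be converted to lines as follows", with the bands "1 line = 3-7 letters read; 2 lines = 8-12 letters read; 3 lines = 13-17 letters read" and so on upwards. The DCNVA rule in the same bullet maps absolute logMAR values to a line number, ending at "14 lines = 0.0 logMAR, 15 lines = -0.1 logMAR, 16 lines = -0.2 logMAR, and 17 lines = -0.3 logMAR".

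SAP 9.1 analyses each responder endpoint "using a logistic regression with treatment and Baseline included as independent factors" and reports "the percentage of subjects (or eyes) in each treatment group meeting the criteria, the odds ratio (OR) with 95% CI". Protocol 4.1 gives the same line thresholds without any letter-to-line rule. Protocol 9.3.1 says of the secondary endpoints that "the p-values for those analyses will be considered descriptive". Mean change in BCDVA is a separate secondary endpoint, analysed by ANCOVA.

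**The concern.** The trial collects whole letters, then discards that precision before taking the change. If Baseline and follow-up scores are each rounded to a line, the difference depends on where in a 5-letter band the subject started. A smaller gain can count while a larger one does not.

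The SAP does not say outright whether the visit score or the change is banded. Two features favour the visit score: what is converted is the collected number of letters read, and the parallel DCNVA list is of absolute scores. On the other reading the dependence on starting score disappears, but gains short of 5, 10 and 15 letters still earn 1, 2 and 3 lines.

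At stake is what the reported percentages mean. A reader will take a ≥1-line improver to be someone who gained a full line. Improving visual performance is a stated objective, so these tables will be read.

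**Working it through.** **Inputs.** The bands and thresholds come from SAP 4.2.2. SAP section 6 states "A sample size of 36 total completed subjects is needed for the study", which at 1:1 allocation is 36/2 = 18 per arm. The 5-letter line is inferred from the band width; no visible text states it. No SD of letter change is given, so 3, 4 and 5 letters are assumed.

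**Reproducing the bands.** line(x) = floor((x + 2)/5) gives 0–2 → 0, 3–7 → 1, 8–12 → 2, 13–17 → 3, as the SAP states.

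**Enumeration, visit scores converted.** Line gain = line(follow-up) − line(Baseline), over the five starting positions in a band:

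- gains of 1, 2, 3, 4 letters earn a line from 20%, 40%, 60%, 80% of starting scores; 5 or more always does;
- gains of 6–9 letters earn a second line, and 11–14 a third, in the same 20–80% shares;
- 52 → 53 (+1) is 1 line; 53 → 57 (+4) is 0; 52 → 58 (+6) is 2; 53 → 62 (+9) is 1.

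**Rates with no true change.** Change is taken as normal, mean 0, rounded to whole letters, so P(change ≥ j) = 1 − Φ((j − 0.5)/SD). From the highest score in a band (such as 52) 1 letter is enough; from the lowest (such as 48) 5 are needed. With the five positions equally likely, the ≥1-line rate is the mean of P(change ≥ j) for j = 1 to 5. At SD 3: (43.4 + 30.9 + 20.2 + 12.2 + 6.7)/5 = 22.7%. If the change itself is banded, the rule is change ≥ 5k − 2 for k lines.

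| | SD 3 | SD 4 | SD 5 |
|---|---|---|---|
| ≥1 line, visit scores banded | 22.7% | 27.8% | 31.5% |
| ≥1 line, change banded | 20.2% | 26.6% | 30.9% |
| ≥5 letters | 6.7% | 13.0% | 18.4% |
| ≥1 line, lowest start in band | 6.7% | 13.0% | 18.4% |
| ≥1 line, highest start in band | 43.4% | 45.0% | 46.0% |
| ≥2 lines, visit scores banded | 1.2% | 3.9% | 7.5% |
| ≥10 letters | 0.1% | 0.9% | 2.9% |

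Per 18 completers, the ≥1-line row is 4.1 to 5.7 responders, against 1.2 to 3.3 for ≥5 letters. The share of counted improvers who gained fewer than 5 letters is 1 − (≥5-letter rate)/(≥1-line rate), which from unrounded rates is 71%, 53% and 42%.

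**Does the Baseline covariate help?** The pattern repeats every 5 letters, so a linear term cannot follow it. A logistic fit of the exact SD 3 rates on Baseline scores 33–82 (ten full bands) predicts 20.5–24.9%, where the true rates run from 6.7% to 43.4%.

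**The case against.** The strongest objection is that the per-visit reading is an inference. The conversion sentence follows directly on the words about improvement from Baseline, and the bands spelled out are exactly those for 1, 2 and 3 lines. If the change is banded, the 52 → 53 example, the spread by starting position and the Baseline-covariate check all fall away. The distance-acuity equipment and procedure cells are blacked out and might bear on this. That uncertainty stands. But the visible text says the letters read are converted, nothing visible says the change is, and on either reading a gain under 5 letters can count as a line.

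Second, nearest-line rounding is fixed in advance and identical in both arms, and no visible text defines a line gain as 5 letters. It favours neither arm, and small losses can be turned into line losses in the same way. This is right, and it limits the harm to misclassification. It does not explain why +1 should count when +4 does not.

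Third, the size depends on assumed SDs. The ratio of rates falls from 22.7/6.7 = 3.4 at SD 3 to 31.5/18.4 = 1.7 at SD 5; at SD 6 it would be 34.3/22.7 = 1.5. It shrinks but does not vanish.

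Fourth, secondary p-values are descriptive, the continuous BCDVA analysis is planned, and all the data will be listed. These points make the issue modest. They do not correct the responder tables.

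**Conclusion.** The concern holds. As written, the conversion rounds each visit's letters to the nearest line, so equal gains are classed differently and gains below 5 letters can be reported as a line. With no true change, the ≥1-line rate is about 13 to 16 percentage points above the ≥5-letter rate (31.5 − 18.4 = 13.1 at SD 5; 22.7 − 6.7 = 16.0 at SD 3), or roughly two to three extra responders among 18.

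This rests on a 5-letter line, assumed SDs of 3 to 5 letters, evenly spread starting positions, and the per-visit reading. Under the change reading the ≥1-line rates are nearly as high, but the dependence on starting score goes. Type I error, the primary IOP endpoint and the BCDVA change ANCOVA are unaffected. The SAP should be corrected, but this does not threaten the trial's main conclusion.

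**What to change.** Before unmasking, replace the BCDVA banding in SAP 4.2.2 with: *BCDVA responders are subjects (or eyes) whose change from Baseline in letters read is ≥5 (1 line), ≥10 (2 lines) or ≥15 (3 lines). If an arm has no responders, counts and percentages are reported without an odds ratio.* This settles both readings. No change to the DCNVA rule is proposed.

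The cost is SAP wording and one derived variable from data already collected. Three consequences should be accepted openly; the figures assume a 3-letter benefit, 18 per arm and SD 3, 4, 5.

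- Responder percentages will be lower.
- Power for the ≥1-line comparison (unadjusted chi-square, two-sided 5%) falls from 58%, 41%, 31% under the visit-score bands to 47%, 34%, 26%. The planned analysis of BCDVA change has 83%, 59%, 42% (as a t-test without covariate), more than either responder rule.
- The chance that at least one arm has no ≥2-line responder, 1 − (1 − (1 − p₀)¹⁸)(1 − (1 − p₃)¹⁸) with p₀ and p₃ the response rates at mean change 0 and 3, rises from 85%, 52%, 26% to 99.7%, 91%, 66%. At ≥3 lines it is about 94% or more under either rule.

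Since an odds ratio may not be estimable with an empty cell, the zero-responder sentence is needed whichever rule is kept.
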